## 9.2 SETTING

See [section 9.11](#) below.

## 9.3 VARIABLES

### 9.3.1 Exposures

The exposure variables in this study include Tio initiation, and ICS/LABA dose increase or an additional prescription/refill of high-dose-ICS/LABA following the first prescription of baseline high dose ICS/LABA for at least 3 months.

### 9.3.2 Outcomes

#### 9.3.2.1 Primary outcomes

*(Database I/II combined)*

The primary outcome measure is time to first exacerbation per person. Exacerbations will be defined as either a hospitalization with a primary diagnosis of asthma, an ER visit with a primary diagnosis of asthma, an asthma exacerbation diagnosis recorded (ICD 493.02, 493.12, 493.22, 493.92, J45.21, J45.31, J45.41, J45.51, J45.901). The primary endpoint analysis will be of patients aged 12 years and above.

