### **9.1 STUDY DESIGN**

Data extraction from both databases (I and II, see [section 9.4](#)) will be conducted by

. All patients will be required to have a prescription for ICS/LABA therapy [e.g. Advair (Diskus and HFA), Airduo, Breo, Dulera, or Symbicort]. The date of the first prescription of ICS/LABA within the study period (Jan 1st 2016 to Nov 30th 2018) will be defined as ICS/LABA-initiation (ICS/LABAi) date. This baseline cohort will then be followed to identify two cohorts (two arms of the study). One cohort that receives a prescription for Tiotropium Respimat® 1.25 mcg (on top of baseline ICS/LABA) will be classified as the ‘Tio’ group, and the second cohort that receives a “step-up” from baseline low-dose ICS/LABA to medium/high dose ICS/LABA or from baseline medium dose ICS/LABA to high dose ICS/LABA or an additional prescription/refill of high-dose-ICS/LABA following the first prescription of baseline high dose ICS/LABA within the study period, will be classified as the ‘NonTio’ group. The date of the first prescription for Tiotropium Respimat® 1.25 mcg in the ‘Tio’ group will be defined as the index date for the ‘Tio’ group. Similarly the date of the first prescription for a “step-up” from baseline low-dose ICS/LABA to medium/high dose ICS/LABA or from baseline medium dose ICS/LABA to high dose ICS/LABA or an additional prescription/refill of high-dose-ICS/LABA following the first prescription of baseline high dose ICS/LABA (evidenced by at least 90-days of prescription utilization) within the study period will be defined as the index date for the ‘NonTio’ group.

Patients will be required to have a minimum follow-up period of 30 days after the index date for the analyses of the primary endpoint with no limit on the maximum period (this 30-day minimum follow-up period requirement will be waived in a sensitivity analysis). Subject to sample size requirements, patients will be required to have available records for at least 12 months prior to the index date to ensure no prior use of Tiotropium Respimat® and to establish baseline patient characteristics. This 12-month period prior to the index date will be defined as the pre-index period.

Figure 9.1.1 Study Design

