## **9.9 LIMITATIONS OF THE RESEARCH METHODS**

Claims and EMR data are subject to certain limitations. The presence of a claim for a filled prescription or prescription absent a claim does not indicate that the medication was consumed or that it was taken as prescribed, and any medications filled over-the-counter or provided as samples by the physician will not be observed in the claims data. Finally, as with all claims-based analyses, study results may not be generalizable to the overall population as patients who have commercial health insurance may be different from those with non-commercial or without (commercial) health insurance. Database I underrepresents the population aged 65 years and older, which may affect external validity in the case of Medicare, Medicare Advantage or Medicaid patients. Since unmatched patients will be excluded, the results may not be generalizable to all patients. Some study measures and outcomes will include missing data and hence reduce the sample size. Not all patients in Database II will have lung function results or ACT scores, therefore, the sample size for related secondary endpoints or sub-group analyses may produce results for these analyses that are not generalizable. While duplication analyses will make double counting the same patient across both datasets negligible, it should be noted that the same patient may be present in both cohorts.

Including patients with persistent use of high-dose ICS/LABA (as opposed to an increase in ICS/LABA dose) in the NonTio group, may complicate the interpretation of the results, as patients with a deterioration in their asthma necessitating an increase in asthma medication (Tio group) will be matched to patients continuing on the same medication (high-dose ICS/LABA).

No claims regarding the effectiveness of Tio should be made on the basis of this study. This real-world evidence study lacks controls available with randomized controlled trials. Patient misclassification, missing data, objective and reliable measurement of patient outcomes, and lack of detailed information regarding subjects' clinical history or clinical status during the study timeframe may undermine the accuracy of our study results.

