## 9.12 BIAS

### Channeling Bias Mitigation

Introduction of channeling bias in this study is highly likely using retrospective claims data based on asthma medication use; patients between the two cohorts may differ in baseline control and severity levels. On aggregate, patients for whom Tiotropium Respimat® 1.25 mcg was added (vs NonTio) are likely to be less well-controlled and more severe both at baseline and during the follow up period. Absent a method to control for this channeling bias, it is likely that placing sicker patients in the Tiotropium Respimat® 1.25mcg group will confound an accurate comparison of cost, resource use, and other outcomes between the groups. Two design features of our study will help mitigate this bias. First, our comparison (NonTio) group will be required to step-up their baseline ICS/LABA dose or have an additional prescription/refill of high-dose-ICS/LABA following the first prescription of baseline high dose ICS/LABA within the study period. Second, we will use Propensity Score Matching (PSM) to match patients on key measures of disease control and severity as listed in [Table 1](#), such as demographics, Charlson Comorbidity Index (CCI) score, specific comorbidities, number of prescriptions (overall and asthma-related medications). This baseline matching strategy will be particularly important to ensure that patients in the TIO group who have a corresponding increase in their ICS dose at or prior to the date of their TIO prescription (for example, if the patient has an exacerbation), will be matched to a corresponding NonTIO patient in terms of increased ICS dose or additional ICS prescription. It should be noted that after the prescription index date for both Tio and NonTio patients, we anticipate changes in ICS medication for patients in both cohorts. These ICS medication changes reflect patient

outcomes in the follow-up period, where patients who encounter exacerbation in either group are likely to see a change in the ICS dose.

As a result, post-index period ICS medication changes will not alter the classification of patient groups nor will it be the basis for exclusion of these patients.

We will conduct 1:2 matching using a nearest neighbour matching approach with a radius of  $0.2 * SD(\log(P))$ . This will be conducted in both databases (IMS: Cohort I and EMRClaims+: Cohort II) separately.

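### No rule separates the episode that prompted escalation from the first outcome event, so its continuing claims can be scored as the first exacerbation, at a rate expected to be higher in Tio

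*Combined protocol and SAP*

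**What the plan says.** The outcome. Section 9.3.2.1: "The primary outcome measure is time to first exacerbation per person". An event is an admission or ER visit whose primary diagnosis is asthma, or "an asthma exacerbation diagnosis recorded" under a list of ICD codes. The code limb is restricted neither by care setting nor to a new episode.

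The start of follow-up. In section 9.1 the Tio index date is "The date of the first prescription for Tiotropium Respimat® 1.25 mcg". The NonTio index date is either "the date of the first prescription for a “step-up” from baseline low-dose ICS/LABA to medium/high dose ICS/LABA" (or the corresponding medium-to-high step), or "an additional prescription/refill of high-dose-ICS/LABA following the first prescription of baseline high dose ICS/LABA (evidenced by at least 90-days of prescription utilization". The section then says: "Patients will be required to have a minimum follow-up period of 30 days after the index date for the analyses of the primary endpoint". The only sensitivity analysis on those 30 days waives the minimum.

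Why patients reach index. Section 9.9 describes "patients with a deterioration in their asthma necessitating an increase in asthma medication (Tio group") being matched to patients who continue high-dose ICS/LABA. Section 9.12 allows for an ICS increase at or before the Tio date, for example "if the patient has an exacerbation", and expects Tio patients to be less well controlled.

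Matching. Table 1 uses the presence of asthma-related admissions, visits or OCS use over the pre-index period, and the ICS/LABA dose level at the first prescription. It does not use how recent an event was.

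**The concern.** An exacerbation that leads to a new prescription often generates several claims: the visit itself, a discharge, a follow-up visit still coded as an exacerbation. If one of these is dated on or just after index, nothing in sections 9.3.2.1 or 9.7.1 stops it from being the patient's first event. Such an event cannot have been influenced by the index treatment, and it falls at the very start of follow-up.

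The comparison is distorted further if the groups enter follow-up at different points in an episode. Tio and step-up NonTio patients are escalated at index. Refill NonTio patients need only a continuing prescription. Any mix of the two in NonTio puts a lower carry-over rate there than in Tio, which pushes the HR toward or past 1.

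**Working it through.** **1. Does any existing rule close the gap?** The 30-day requirement decides who is analysed, not which events count, and its sensitivity analysis removes it. Matching on presence over the pre-index period treats an admission 11 months before index like a discharge the day before. Covariate adjustment (section 9.7.1) cannot remove a claim already counted as the outcome. Section 9.1 places baseline before index and follow-up after it, which leaves index-day records undefined.

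**2. The plan's power figures, as a check on the inputs.** Section 9.5 gives 2,100 Tio and 4,200 NonTio, hazards of 0.012 vs 0.0096 per month (first scenario) and 0.028 vs 0.0224 (second), so HR 0.80. Alpha is not stated; I assume two-sided 0.05.

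Events: d = 2,100(1 − exp(−0.8λT)) + 4,200(1 − exp(−λT)). Power = Φ(|ln 0.80|·√(d·⅓·⅔) − 1.96).

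- First scenario, T = 5.5 months: d = 376, power 53% (stated 77%).
- Second scenario, T = 11 months: d = 1,572, power 98.6% (stated 98%).
- T = 10 months in both: d = 667 and 1,447, power 77.5% and 97.9%.

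Both stated figures are recovered at a common follow-up of about 10 months, which the plan does not state. They are not in dispute here.

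**3. Where carry-over claims fall.** Let q be the share of escalating patients with a carry-over claim and r the refill share of NonTio, taking refill patients to have none. Tio has 2,100q such events and NonTio 4,200q(1 − r). At q = 2%:

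| r | Tio events | NonTio events | Rates, Tio vs NonTio |
|---|---|---|---|
| 0 | 42 | 84 | 2% vs 2% |
| 0.5 | 42 | 42 | 2% vs 1% |
| 0.75 | 42 | 21 | 2% vs 0.5% |
| 1 | 42 | 0 | 2% vs 0% |

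The Tio rate is higher for any r above 0. Tio holds the majority of events only if r exceeds one half.

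**4. Effect on the HR.** Let a share q_g of group g have a carry-over claim spread evenly over the first 14 days (w = 0.46 months), on top of the plan's constant hazard:

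S_g(t) = (1 − q_g·min(t, w)/w)·exp(−λ_g t).

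The observed HR is e^β, where β solves the expected Cox score equation with 2,100 and 4,200 patients. With a true HR of 0.80:

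| Tio vs NonTio | 0.012/month, 5.5 months | 0.012/month, 11 months | 0.028/month, 11 months |
|---|---|---|---|
| none | 0.80 | 0.80 | 0.80 |
| 2% vs 2% | 0.85 | 0.83 | 0.81 |
| 2% vs 1.5% | 0.90 | 0.86 | 0.83 |
| 2% vs 1% | 0.97 | 0.89 | 0.84 |
| 2% vs 0.5% | 1.04 | 0.93 | 0.86 |

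Hand check by the ratio of cumulative hazards, (λ_T·T − ln(1 − q_T)) / (λ_C·T − ln(1 − q_C)). At 2% vs 1%, 0.012 per month and 5.5 months this is (0.0528 + 0.0202)/(0.0660 + 0.0101) = 0.96, against 0.97 in the table.

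At 10 months and q = 2%, the HR for r = 0, 0.5 and 1 is 0.83, 0.90 and 0.98 in the first scenario and 0.815, 0.85 and 0.88 in the second. To reach 1.0, q must be 4.3% (r = 0.5) or 2.2% (r = 1) in the first scenario, and 9.0% or 4.8% in the second. At r = 0 it never reaches 1.

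**5. Why small shares matter.** At 0.012 per month the genuine two-week risk is 1 − exp(−0.012 × 0.46), or about 0.6%. A 2% carry-over is more than three times that.

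**6. Effect of a landmark.** Starting at-risk time after the 14-day window returns HR 0.80 in every case tried, because carry-over is confined to the window by assumption. At 10 months, a day-30 landmark lowers expected events from 667 to 598 (power 77.5% to 73%) and from 1,447 to 1,287 (97.9% to 96.5%).

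**The case against.** A reader might infer that carry-over events fall mostly in Tio. The documents do not support that. The low- and medium-dose NonTio routes are themselves escalations, and section 9.12 presents the step-up requirement as a safeguard against channeling. With equal carry-over among escalators, a Tio majority needs refills above half of NonTio, and no share is given. A higher q in Tio would lower that threshold, but the plan does not quantify it.

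Matching also does more than nothing. Table 1 includes starting dose, and the refill route requires a high-dose start. To the extent that dose is balanced, the asymmetry sits among patients who started on high dose. The section 9.9 sentence concerns exactly those comparators and is already disclosed as a limitation. The section 9.12 example comes from a sentence describing how Tio patients with an ICS increase will be matched, so it is partly a mitigation.

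A reader might also infer that the estimate will be reversed. That rests on assumed rates. An HR above 1 appears in the table only at 2% vs 0.5% with 5.5 months of follow-up. That rate pair implies 75% refills under equal carry-over, and 5.5 months is the source trial's period, whereas section 9.1 sets no maximum. An episode that ended before index with no later qualifying claim is never counted.

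These points limit the size and the asymmetry. They do not supply the missing rule. Disclosure does not change what is scored, and even equal carry-over moves the HR toward 1.

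**Conclusion.** The concern holds in this form: as written, the plan can score continuing claims from the escalation episode as the first exacerbation, in Tio and in step-up NonTio patients. The rate is expected to be higher in Tio whenever NonTio contains refill patients. That time runs from index is a strong inference from section 9.1; sections 9.3.2.1 and 9.7.1 do not state it.

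The direction is toward or past 1, against Tio. The size cannot be fixed from the documents. Under the assumptions above it runs from slight dilution (0.81 to 0.85 at 2% vs 2%), through 0.84 to 0.97 at 2% vs 1%, to 0.86 to 1.04 at 2% vs 0.5%. These figures assume a true HR of 0.80, constant hazards and carry-over confined to 14 days. Because the primary endpoint is affected and the remedy is cheap, the rule should be set before outcomes are analysed.

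**What to change.** In sections 9.3.2.1 and 9.7.1, state for both groups identically that:

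- time zero is the day after index for every patient;
- exacerbation records on the index date belong to baseline;
- a record within 14 days of a qualifying record dated on or before index is part of the baseline episode and is not an outcome.

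Add sensitivity analyses with a 0-day gap and with a common landmark, at-risk time starting at day 14 and at day 30 for all patients and excluding those with an event before it. The landmark runs matter because the 14-day rule leaves at-risk time running while some patients' records are set aside, possibly more often in one group. The 14 days is a judgement, which the alternative gaps test.

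Report the comparison separately for step-up and refill NonTio patients, with the number in each. This shows r and the asymmetry directly.

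Cost: protocol wording and reruns on data already held. A few genuine early events are lost (about 0.6% of patients per two weeks at 0.012 per month), and power falls slightly in the landmark runs, as shown in the working.

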### **9.3.3 Covariates**

Other covariates are described in [Table 1](#), including demographic information as available in the dataset as recorded at index date. Comorbidities included in the CCI will be identified during the pre-index period. Other and specific comorbidities such as cardiovascular conditions, cerebrovascular diseases, hypertension, diabetes, metabolic and endocrine comorbidities, anxiety and depression, gastro-esophageal reflux disease, cancer and obesity will also be identified during baseline. Additionally, polypharmacy at baseline, will be identified in the pre-index period. Finally, a composite measure of asthma control status will be made as defined in Table 1, classified as Well and Poor. Asthma Control Test score and eosinophil blood count levels as available, will also be identified at baseline for Cohort II only. We will also record exacerbation rate, resource use parameters, and cost during baseline.

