## **9.5 STUDY SIZE**

The expected number of asthma patients aged 12 years and above, without concurrent COPD, and continuous enrollment for 12 months prior to the Tiotropium Respimat® date is estimated to be approximately 2,100 to be matched to double (4200 patients) the number of NonTio patients resulting in a total N =6,300. Power calculation was conducted for the primary endpoint, time-to-first exacerbation by the end of the follow-up time. The calculation was based on detecting a significant treatment effect using Cox proportional hazard model. Estimates were obtained from the MEZZO trial comparing tiotropium 2.5 µg vs. salmeterol ([P15-01655](#)). Assuming 6.4% of patients in the control group followed

up for 5.5 months will have an exacerbation (based on the salmeterol group in the MEZZO study) and assuming a constant hazard rate, equating to an exponential rate parameter of 0.012 per month for the control group and 0.0096 per month for the Tio group, the power is calculated to be 77%. Using the Primo study, assuming 26.9% of patients in the control group followed up for 11 months will have an exacerbation (based on the Tio R 5 group in the 48-week study Primo) and assuming a constant hazard rate, equates to an exponential rate parameter of 0.028 per month in the control group and 0.0224 per month in the Tio group, the power is 98%. The Mezzo-derived power calculation likely underestimates the power since our study design includes sicker patients that required a step-up in ICS treatment (not required in the Mezzo Study). While we expect that the actual power will lie between the two estimates (assuming that the patient population is similar to the less severe Primo patients and the more severe MEZZO patients), the estimated power is greater than 77%.

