## 9.11 SUBJECTS

1. Patients with least one asthma diagnosis in the inpatient setting or at least two separate instances of asthma diagnosis (separated by at least 30 days) recorded in the outpatient or emergency room setting will be included (ICD 9 CM: 493.xx or ICD 10: J45-J45.999).
2. Patients will be required to be already on ICS/LABA.
3. Patients below the age of 6 years on the ICS/LABAI date will be excluded.
4. Patients will be required to have available records 12 months prior to the index date (6 months will be used if patient exclusions due to this criteria adversely affect the study sample size).
5. Patients with a diagnosis of COPD at any time during the study period will be excluded.
6. Those who are on biologics at baseline will be removed.
7. After the PSM process, unmatched patients will be excluded.

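### The exacerbation code list omits the status asthmaticus codes, so such a record is not an event unless it falls in an admission or ER visit with asthma as primary diagnosis

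*Combined protocol and SAP*

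**What the plan says.** Section 9.3.2.1 sets the primary endpoint: "The primary outcome measure is time to first exacerbation per person". An event can arise in three ways. Two depend on setting and diagnosis position: "either a hospitalization with a primary diagnosis of asthma, an ER visit with a primary diagnosis of asthma". The third depends on neither: "an asthma exacerbation diagnosis recorded (ICD 493.02, 493.12, 493.22, 493.92, J45.21, J45.31, J45.41, J45.51, J45.901". The list is closed, with no wildcard and no indication that the codes are examples.

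Section 9.11 defines asthma for inclusion by the whole code families: "ICD 9 CM: 493.xx or ICD 10: J45-J45.999".

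No separate exacerbation definition is given for the secondary rate (9.3.2.2), for the Kaplan-Meier proportions at 6 months and one year (9.7.1), or for the pre-index period, where 9.3.3 says: "We will also record exacerbation rate, resource use parameters, and cost during baseline". The 9.3.2.1 definition presumably applies to all of them.

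**The concern.** The code-based route picks up attacks that are not a primary-diagnosis admission or ER visit. Within each asthma family it names one code, the one for (acute) exacerbation, and leaves out the neighbouring code for status asthmaticus, which marks a more severe attack. For records that reach the endpoint only by this route, the milder coded attack is an event and the more severe one is not. The plan gives no reason for this, and status asthmaticus is mentioned nowhere.

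What is at stake is the validity of the primary event definition and of the outcomes that share it. A missed record leaves the patient event-free or moves the first event to a later date. The baseline exacerbation rate could be miscounted in the same way. It is not a matching parameter in Table 1, but under 9.7.1 unbalanced baseline characteristics enter the regression.

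**Working it through.** **1. Codes by family.** The documents print no code labels; the meanings below are those of the ICD code sets in which the endpoint is written.

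| Family | Listed in 9.3.2.1: (acute) exacerbation | Not listed: status asthmaticus |
|---|---|---|
| 493.0x | 493.02 | 493.01 |
| 493.1x | 493.12 | 493.11 |
| 493.2x | 493.22 | 493.21 |
| 493.9x | 493.92 | 493.91 |
| J45.2x | J45.21 | J45.22 |
| J45.3x | J45.31 | J45.32 |
| J45.4x | J45.41 | J45.42 |
| J45.5x | J45.51 | J45.52 |
| J45.90x | J45.901 | J45.902 |

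Nine are listed and nine are missing. All eighteen lie inside the inclusion range of 9.11.

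**2. The rule applied literally.** These are constructed records, each assumed to carry only the asthma code shown.

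| Record | J45.51 | J45.52 |
|---|---|---|
| Admission or ER visit, asthma primary | event | event |
| Admission with another primary diagnosis (such as respiratory failure), asthma code secondary | event | no event |
| ER visit, asthma code secondary | event | no event |
| Office or urgent-care visit | event | no event |

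The gap is confined to the last three rows.

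**3. Size of the loss (assumed).** The documents give no frequencies. Suppose a share s of 2% to 10% of exacerbation-level encounters carries a status asthmaticus code, and a share q of 20% to 50% of those falls outside the primary-diagnosis routes. The missed share is s × q: from 0.02 × 0.20 = 0.4% to 0.10 × 0.50 = 5%. Treating every missed record as a lost first event gives an upper bound, because some are only delayed.

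**4. Power.** Inputs from 9.5: "approximately 2,100 to be matched to double (4200 patients) the number of NonTio patients", and hazard ratio 0.0096/0.012 = 0.0224/0.028 = 0.80. Two-sided 0.05 is assumed, since no level is stated.

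- Events: d = 4,200(1 − exp(−λc·T)) + 2,100(1 − exp(−λt·T)).
- Power (Schoenfeld): Φ(√(d × 1/3 × 2/3) × |ln 0.80| − 1.96).

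The plan's own figures first. With 0.028 and 0.0224 per month over 11 months, d = 1,113 + 459 = 1,572. Power is 98.6% (Schoenfeld) or 98.0% (Freedman), which matches the stated 98%. With 0.012 and 0.0096 over 5.5 months, d = 376 and power is 50% to 53%. The stated 77% is approached only at 11 months: d = 730, 77.9% (Freedman) or 81.1% (Schoenfeld). That discrepancy is a separate question and does not bear on this point. Solving back from 77% gives (1.960 + 0.739)² / [(2/9)(ln 0.80)²] = 658 events.

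Effect of losing 5% of events, on each basis (Schoenfeld):

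| Events | Power, none lost | Power, 5% lost |
|---|---|---|
| 376 | 53.2% | 51.1% |
| 658 | 77.0% | 74.9% |
| 730 | 81.1% | 79.1% |
| 1,572 | 98.6% | 98.2% |

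The largest fall is 2.1 points. A 1% loss moves 81.1% to 80.7%, so the lower end of the range has almost no effect.

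**5. Hazard ratio.** If a share s of control events is missed, the true overall ratio is 0.80 and the missed events have ratio h, the observed ratio is about (0.80 − s·h)/(1 − s).

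| Share missed | h = 0.6 | h = 0.8 | h = 1.0 |
|---|---|---|---|
| 5% | 0.81 | 0.80 | 0.79 |
| 10% (twice the upper end assumed) | 0.82 | 0.80 | 0.78 |

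The sign depends on h, about which the documents say nothing.

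**The case against.** The strongest reply is that the definition already catches most of these attacks. Any admission or ER visit with asthma as primary diagnosis counts, whichever asthma code is used. This stands, and it limits the point to secondary-position and outpatient records. It does not remove the point, because the code-based route exists for such records.

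Second, the reading needs the ICD labels, which the documents do not print, and it assumes that a status asthmaticus record is not accompanied by a listed exacerbation code. The labels are the vocabulary in which the endpoint is written, so relying on them is fair. The second part stands as a caveat: where a listed code appears on the same encounter, nothing is lost; where it appears later in the episode, the event is only delayed.

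Third, wider inclusion codes than event codes are normal, since uncomplicated asthma codes also qualify a patient without being events. This is right. Section 9.11 shows that the plan regards these codes as asthma; it does not contradict 9.3.2.1.

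A reader might also infer that the omission favours Tio, because 9.12 expects Tio patients to be more severe. The documents do not support that. The same section introduces the step-up or high-dose comparator and matching on control and severity, and the analysis is of matched patients. More severe patients may also have more primary-diagnosis admissions and ER visits, which are captured.

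**Conclusion.** The point holds as a gap in the primary event definition. Applied literally, 9.3.2.1 does not count a status asthmaticus code recorded in a non-primary position or at an outpatient encounter, although it counts an exacerbation code in the same place. This rests on the closed list, the standard ICD code meanings, and the absence of a listed code on the same encounter.

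The consequences are probably modest. The affected records are likely a minority. On the assumed 0.4% to 5% of events missed, power falls by about two points at most. The documents do not support a count of lost first events, since a missed record may only delay the first event and no code frequencies are given. Nor do they support a signed bias: with equal effects in missed and captured events the hazard ratio is unchanged, and otherwise it can move either way. The reason to correct it is that the endpoint should not exclude a more severe coded attack where it counts a milder one.

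**What to change.** In 9.3.2.1, extend the list to 493.01, 493.02, 493.11, 493.12, 493.21, 493.22, 493.91, 493.92, J45.21, J45.22, J45.31, J45.32, J45.41, J45.42, J45.51, J45.52, J45.901 and J45.902. State that the same definition applies to the secondary exacerbation rate, the Kaplan-Meier proportions and the baseline exacerbation rate in 9.3.3. If the codes were left out on purpose, give the reason and pre-specify a sensitivity analysis that includes them.

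The cost is one line of protocol text and a longer code list in the program, with no new data or patients. The downside is a slightly broader event definition. The change should be made before outcomes are examined.
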